7.5.1 Primary Analysis of Progression-Free Survival

The primary objective of this study is to compare PFS (based on the primary definition) across the two randomized arms. A two-sided $\alpha = 0.2$ log-rank test, stratified by number of lines of prior therapy (2-3 vs. ≥ 4) and ISS Staging at study entry (I-II vs. III) will be used to compare the PFS of subjects randomized to E-Pd to that of subjects randomized to Pd.

A stratified Cox proportional hazard model for PFS with treatment arm as single covariate will be used to report the hazard ratio of E-Pd to Pd and its corresponding 80% (and 95%) CI. The stratification factors will be the same as those used in the randomization.

The PFS function for each treatment arm will be estimated using the KM product limit method and will be displayed graphically. Median PFS will be estimated via the KM curve. Two-sided 95% CI for the median PFS will be computed for each randomized arm by the Brookmeyer and Crowley method using the log-log transformation of the survivor function.

The method of Gail and Simon¹² will be used to test for a qualitative interaction between treatment and strata, number of lines of prior therapy (2-3 vs. ≥ 4) and ISS Staging at study entry (I-II vs. III). This test will be conducted at the $\alpha = 0.10$ level and using the HR as estimate for treatment effect.

The proportional hazards assumption will be assessed via the following hazard rate model, which contains a time dependent covariate:

$$\lambda(t, z) = \lambda_i(t) e^{\{(b_1 + b_2 \times [\log(t)]) \times Z\}}, \quad i = \{1 - 4\}$$

where $i = 1 - 4$ corresponds to each of the four levels the stratum can take, and Z is the treatment indicator, which is equal to 1 for the combination arm and 0 for the control arm. The transformation of time is $\log(t)$. The null hypothesis, that the proportional hazards assumption is valid, i.e., that $b_2 = 0$, will be tested against the alternative hypothesis that $b_2 \neq 0$ using a Wald statistic.

Sensitivity analyses of PFS will also be conducted based on the secondary definition of PFS. These analyses will be the same as those specified above in [Section 7.5](#), Primary Analysis of PFS.

7.5.1.1 Supportive Analyses of Progression-Free Survival

The following supportive analyses will be conducted using both the ITT and the secondary definitions of PFS. P-values provided for these analyses are descriptive and will be used to evaluate the results in context of the primary analyses.

- 1) A multivariate Cox regression model will be used in order to estimate the treatment effect after adjustment for possible imbalances in known or potential prognostic factors. The factors used in the randomization, which, by definition, will be balanced across arms, will still be included in the model as stratification factors. However, all additional factors will be incorporated as covariates. The additional factors, which are all measured at baseline, will include: age (< 75 vs. ≥ 75), gender (male vs. female), ECOG PS (0-1 vs. 2), prior stem cell transplantation (yes vs. no), high myeloma risk (yes vs. no) [see [Section 7.5.1.2](#) for details], time from initial diagnosis, creatinine clearance (<60ml/min vs. ≥ 60 ml/min), and LDH (< 300IU/L, ≥ 300 IU/L).

The level of the covariate normally associated with the worst prognosis will be coded as the reference level:

- Age: ≥ 75
- Gender: Female
- ECOG: 2
- Prior stem cell transplantation: Yes
- High myeloma risk: Yes
- Time from initial diagnosis (\geq median)
- Creatinine clearance: < 60 ml/min
- LDH (≥ 300 IU/L)

The p-value associated with treatment and with each of the baseline covariates will be presented. The hazard ratio along with the associated 95% CI will also be presented. In addition, an 80% CI will be provided for the treatment effect.

- 2) PFS using stratification factors as obtained from the baseline CRF pages (instead of IVRS). The p-value and the hazard ratio associated with treatment will be presented along with the associated 2-sided 80% and 95% CIs. This analysis will be performed only if there is a difference of 10% in strata between the IVRS and CRF pages.
- 3) PFS using an un-stratified log rank test. The p-value and hazard ratio associated with treatment will be presented along with its associated two-sided 80% and 95% CIs.
- 4) PFS using an unstratified Cox proportional hazards model, adjusted, using as covariates only the two stratification factors used in randomization. The p-value and hazard ratio associated with treatment will be presented along with its associated two-sided 80% and 95% CIs.
- 5) PFS for subjects with no relevant deviation. These analyses will be conducted only if there are more than 5% subjects with relevant protocol deviations. The p-value and hazard ratio associated with treatment will be presented along with its associated two-sided 80% and 95% CIs.

A by-subject listing will be presented including treatment arm, PFS duration under the primary definition, PFS duration under the secondary definition, whether the subject was censored under the primary definition, and if censored, the reason, and whether the subject was censored under the secondary definition, and if censored, the reason.

7.5.1.2 Subset Analyses of Progression-Free Survival

The influence of baseline and demographic characteristics on the treatment effect will be explored via exploratory subset analyses for the following factors:

- Age (< 75 years, ≥ 75 years)
- Age (< 65 years, ≥ 65 years)
- Race (White, Black, Asian, Other)
- Gender (Male, Female)
- Baseline $\beta 2$ microglobulin (mg/L) (< 3.5 , ≥ 3.5)

- ISS Stage at study entry (I-II, III)
- Baseline LDH (< 300IU/L, ≥ 300IU/L)
- Baseline creatinine clearance (ml/min) (< 60, ≥ 60)
- Number of lines of prior therapy (2-3, ≥4)
- Region (North America, Europe, Japan, And Australia)
- Baseline ECOG performance status (0-1, 2)
- Prior stem cell transplant (Yes, No)
- Myeloma risk category (High risk, Low risk and Other)
 - High risk: ISS stage II or III **and** t(4;14) or del(17p) abnormality
 - Low risk: ISS stage I or II **and** absence of t(4;14), del(17p) and 1q21 abnormalities **and** age < 55 years
 - Standard risk: any subjects not meeting the definition of high or low risk and enough data to be classified as standard risk
- Individual FISH abnormalities (del 17p, t(14; 16), t(4; 14), del(1q), and del(1p))

The hazard ratio of E-Pd to Pd and the associated 95% CI for each subgroup category will be presented in a forest plot. The estimate of each hazard ratio and CI will be generated using an unstratified Cox proportional hazards model with treatment as the only covariate.

7.5.2 Analysis of Objective Response

The number and percentage of subjects in each category of best overall response per investigator assessment (stringent complete response [sCR], complete response [CR], very good partial response [VGPR], partial response [PR], minor response [MR], stable disease [SD], progressive disease [PD], or unable to determine [UD]) will be presented by treatment group. An estimate of the response rate and an associated exact two-sided 95% CI (Clopper and Pearson¹³) will be computed, by treatment group.

One of the secondary objectives is to compare the ORR in the two treatment groups using a two-sided $\alpha = 0.2$ level Cochran-Mantel-Haenszel (CMH) test stratified by the same factors used in the analysis of PFS. An estimate of the treatment odds ratio and corresponding two-sided 80% CI will be computed. A two-sided 95% CI will also be computed.

A 2-sided, 80% CI (along with 95% CI) for the difference of ORR between treatment arms will be computed for all randomized subjects by the method of DerSimonian and Laird¹⁴, using a fixed-effects model (setting Δ^2 equal to zero), adjusting for the stratification factors. The weighted response rate difference and 80% CI (along with 95% CI) can be determined using the following formula:

$$\hat{\theta} = \frac{\sum_{i=1}^4 \hat{\theta}_i w_i}{\sum_{i=1}^4 w_i} \sim N(\theta, 1 / \sum_{i=1}^4 w_i)$$

where $\hat{\theta}_i$ is the response rate difference of the i^{th} stratum and $w_i = 1/\text{var}(\hat{\theta}_i)$.

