8.4.2.2 Secondary Efficacy Analysis

Objective response rate is a secondary objective. A two-sided $\alpha = 0.2$ level Cochran-Mantel-Haenszel (CMH) test, stratified using the same factors as in PFS, will be used to compare the response rate between the treatment arms. The response rate, along with its exact two-sided 80% CI, will be computed within each treatment arm. A two-sided, 80% CI for difference of response rate between the treatment arms will also be computed. In addition, the two-sided 95% CI will also be computed.

Overall survival is another secondary objective. It will be compared between arms using a stratified group sequential log-rank test procedure with a two-sided, $\alpha = 0.2$ level. The stratification factors will be the same as those used for the analyses of PFS and tumor response. The OS function for each randomized arm will be estimated using the Kaplan-Meier product-limit method. Median and two-sided, confidence intervals for median OS will be computed by randomized arm.

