5.2 Objective Response Rate

Objective response rate is a secondary objective for this study. With a sample size of 114 subjects, there will be at least 90% power to detect a 23% improvement in response rate, using a two-sided 0.2 level test, in the E-Pd arm (to 58%) compared with a response rate of 35% in the Pd arm.

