7.5 Efficacy

Efficacy analyses (PFS, ORR and OS) will be conducted on the population of all randomized subjects, grouped by arm assigned at randomization, unless otherwise noted.

Unless stated otherwise, whenever a stratified analysis is specified, the stratifications factors will be those used in the randomization (per IVRS), that is:

- Number of prior lines of therapy (2-3 vs. ≥ 4)
- ISS Staging at study entry (I-II vs. III)

The final analysis of PFS will occur after at least 71 progression events have been observed. This analyses will serve as the basis for the clinical study report. The final analysis of OS will be conducted after at least 78 deaths have been observed.

All p-values reported will be 2-sided. The alpha (α) level used for the two-sided CI will be same as nominal significance level for hypothesis testing ($\alpha = 0.2$). In addition two-sided 95% CI for these endpoints will also be provided. The p-values presented in the clinical study report will be rounded to the fourth decimal place. Point estimates and confidence bounds for efficacy variables will be rounded to the second decimal place.

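### The planned 80% CI for the ORR difference covers only about 73-74% at the design rates if the usual unpooled variance is used, and the SAP does not name the variance estimator

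*SAP*

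**What the plan says.** Protocol 8.4.2.2 asks for the interval without a method: "A two-sided, 80% CI for difference of response rate between the treatment arms will also be computed". SAP 7.5.2 supplies one. It specifies "A 2-sided, 80% CI (along with 95% CI) for the difference of ORR between treatment arms", which "will be computed for all randomized subjects by the method of DerSimonian and Laird" with the between-stratum variance set to zero, and adds: "The weighted response rate difference and 80% CI (along with 95% CI) can be determined using the following formula". The formula that follows averages the four stratum differences θ̂ᵢ with weights wᵢ = 1/var(θ̂ᵢ) and treats the result as normal with variance 1/Σwᵢ.

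The strata are the two-by-two combinations of prior lines of therapy (2-3 vs ≥4) and ISS stage (I-II vs III). SAP 7.5 says that "the stratifications factors will be those used in the randomization (per IVRS"), and the hypothesis test for ORR is a CMH "test stratified by the same factors used in the analysis of PFS".

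The planning figures are in SAP 5.2: "With a sample size of 114 subjects, there will be at least 90% power to detect a 23% improvement in response rate", to 58% in the E-Pd arm "compared with a response rate of 35% in the Pd arm".

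The visible text does not say how var(θ̂ᵢ) is estimated, or what happens when that estimate is zero.

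**The concern.** The variance 1/Σwᵢ is right when the weights are fixed. Here each weight comes from the same few responses as the difference it multiplies. A stratum whose observed rates happen to lie far from 50% gets a small estimated variance and so too much weight, and the stated standard error takes that small variance at face value. The interval is then too narrow.

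At 35% vs 58% there is also a bias. A chance-high rate in the E-Pd arm and a chance-low rate in the Pd arm both move away from 50%, so strata with an exaggerated difference are up-weighted.

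If a stratum's estimated variance is zero, its weight is infinite and the formula gives no answer.

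At stake is whether the reported 80% and 95% intervals for the ORR difference mean what they say. Because SAP 7.5 sets the CI level to match α = 0.2, readers will set the 80% interval beside the CMH test.

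**Working it through.** **Inputs from the SAP.** N = 114; rates 35% and 58%, true difference 0.23; four strata; two-sided 80% and 95% levels (z = 1.2816 and 1.96). Average size per arm per stratum: 114/8 ≈ 14.

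**Assumptions not visible in the documents.** 1:1 allocation within strata, four sets of stratum shares (table below), and zero-variance strata dropped.

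**The plan's own figure.** With 57 per arm, the SE of the difference is √[(0.35×0.65 + 0.58×0.42)/57] = √(0.4711/57) = 0.0909. Power at two-sided 0.2 is Φ(0.23/0.0909 − 1.2816) = Φ(1.248) = 89.4%. A pooled-variance calculation gives 88.7% and exact enumeration of the z test 89.8%. The stated 90% is reproduced to within 2 points, so the inputs are being read as the SAP intended.

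**The SAP formula with unpooled variance.** Take var(θ̂ᵢ) = p̂₁ᵢ(1−p̂₁ᵢ)/n₁ᵢ + p̂₀ᵢ(1−p̂₀ᵢ)/n₀ᵢ and the interval θ̂ ± z/√Σwᵢ. Each setting was simulated 200,000 times, with random stratum totals. Bias, SD and SE are in percentage points; the last three columns give coverage of the 80% CI under other choices.

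| Stratum shares | 80% CI covers | 95% CI covers | Bias | True SD | Mean stated SE | n−1 divisor | Pooled within stratum | MH/Sato |
|---|---|---|---|---|---|---|---|---|
| equal | 74.2% | 91.2% | +1.35 | 9.79 | 8.71 | 76.1% | 79.8% | 79.1% |
| .35/.30/.23/.12 | 73.5% | 90.7% | +1.41 | 9.87 | 8.69 | 75.6% | 79.8% | 79.0% |
| .40/.40/.10/.10 | 73.3% | 90.4% | +1.33 | 9.93 | 8.68 | 75.7% | 79.8% | 79.0% |
| .60/.20/.15/.05 | 74.1% | 91.1% | +1.04 | 9.87 | 8.72 | 76.2% | 79.7% | 78.9% |

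**Hand check, equal strata.** The half-width is 1.2816 × 8.71 = 11.16 points. Coverage is about Φ[(11.16 − 1.35)/9.79] − Φ[(−11.16 − 1.35)/9.79] = Φ(1.002) − Φ(−1.278) = 0.842 − 0.101 = 74.1%. With the bias removed it would be 2Φ(11.16/9.79) − 1 = 2Φ(1.140) − 1 = 74.6%. Nearly all the loss therefore comes from the understated SE.

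**Cause.** The unstratified Wald interval on the same data covers 79%, and the stratified formula recovers to 79.6% at ten times the sample size. The problem is estimated weights in small strata, not Wald intervals in general.

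**Equal rates (35% vs 35%).** The bias is zero, but the unpooled 80% CI excludes zero in 24.9-25.8% of trials. MH/Sato excludes it in 20.6-20.9%, and the CMH test rejects in 20.2-20.5%.

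**Other rates.** At 15% vs 30%, coverage is 75.0-75.6% and bias −0.1 to +0.3 point. At 10% vs 20%, coverage is 75.1-76.4% and bias −0.6 to 0.0 point. The undercoverage persists; the direction of the bias does not. With control rates varying by stratum (12% to 55%) and a constant 23-point difference, the 80% CI covers 73.2-74.7%.

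**Zero-variance strata at the design rates.** In the order of the table, the share of trials with at least one is 0.0%, 0.6%, 3.4% and 19.8% under the unpooled variance, and 0.0%, 0.2%, 1.0% and 8.4% under the pooled. Among trials with none, the unpooled 80% CI still covers only 73.2-74.2%, so a zero-variance rule alone would not cure the problem.

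**The case against.** The strongest reply is that the SAP never commits to the unpooled variance. It writes only var(θ̂ᵢ) and cites a method paper. Parts of the SAP are blacked out, and specific tables are deferred to a separate Data Presentation Plan, so the estimator may be fixed elsewhere. The same formula covers 79.7-79.8% with a pooled within-stratum variance, 79.0-79.1% with arm-level rates and 75.6-76.2% with an n−1 divisor. On this view the visible fault is an unnamed estimator, and 73-74% is one branch. This stands as a condition on the number. It does not remove the point: the unpooled variance is the ordinary reading for a rate difference, and coverage should not turn on a choice the plan leaves open.

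The quoted range also rests on assumptions. Over a wider set of stratum mixes and zero-variance rules it is 72.2-75.6%, and under 2:1 allocation 68-71%. Allocation of 2:1 fits the stated ORR power less well (85.8%). The size moves; the direction does not.

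Finally, the consequence is limited. The interval is supplementary, the endpoint is secondary, and no visible decision rule uses it. A bias near 1 point is small against a sampling SD near 10. That is accepted, and it is why this is a correction worth making rather than a threat to the trial's conclusions.

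**Conclusion.** The concern holds. With the unpooled binomial variance, at 35% vs 58% and N = 114, the nominal 80% CI for the ORR difference covers about 73-74% and the nominal 95% CI about 90-91%. The true SD is 9.8-9.9 points against a stated SE of 8.7. The result is conditional on that estimator, on 1:1 allocation and on the assumed stratum shares; undercoverage appeared under every stratum mix and zero-variance rule tried with the unpooled variance. It is not inherent in every variance choice. The CMH test, the odds ratio, the per-arm exact intervals and the PFS analysis are not affected. It should be fixed before analysis.

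**What to change.** In SAP 7.5.2, replace wᵢ = 1/var(θ̂ᵢ) with Mantel-Haenszel weights wᵢ = n₁ᵢn₀ᵢ/(n₁ᵢ + n₀ᵢ), and use the Sato variance for both the 80% and 95% intervals, on the same IVRS strata as the CMH test. With xᵢ the responders, nᵢ = n₁ᵢ + n₀ᵢ and δ̂ the weighted difference:

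- var(δ̂) = (δ̂ΣPᵢ + ΣQᵢ)/(Σwᵢ)²
- Pᵢ = [n₁ᵢ²x₀ᵢ − n₀ᵢ²x₁ᵢ + n₁ᵢn₀ᵢ(n₀ᵢ − n₁ᵢ)/2]/nᵢ²
- Qᵢ = [x₁ᵢ(n₀ᵢ − x₀ᵢ) + x₀ᵢ(n₁ᵢ − x₁ᵢ)]/(2nᵢ)

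This needs no zero-variance rule, has bias under 0.1 point at the design rates, and covers 78.9-79.1% and 94.4%, still slightly under nominal. The cost is one formula and a standard software option. The mean 80% half-width grows from 11.1-11.2 to 11.6 points. No data or design change is needed.

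If the present formula is kept, the SAP should at least name the variance estimator and state a zero-variance rule. A pooled within-stratum variance would restore coverage at the design rates. It still admits zero-variance strata, and at 10% vs 20% with equal strata it covers 77.7% with a bias of −1.0 point, against 79.1% and no bias for MH/Sato.

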7.5.2.1 Subset Analyses of Objective Response

The influence of baseline and demographic characteristics on the treatment effect will be explored via exploratory subset analysis. The subsets will be the same as those analyzed for PFS.

The odds ratio and corresponding 95% CI will be presented for each subgroup in a forest plot.

7.5.2.2 Time to Tumor Response and Duration of Response

The analyses of duration of response will be conducted using the same censoring rules as used in the primary definition of PFS. The distribution of duration of response will be estimated, by arm, using the KM product limit method. The KM estimates will be presented graphically and will present number of events, number of subjects involved, medians along with 95% CIs for the medians.

Time to first tumor response which does not involve censoring, will be summarized by treatment group, using descriptive statistics.

No p-values will be provided for those analyses.

A by-subject listing will be presented including treatment arm, duration of response, whether the subject was censored for duration of response, and, if so, the reason.

7.5.3 Analysis of Overall Survival

Overall survival is another secondary objective. It will be compared between arms using a stratified log-rank test procedure with a two-sided, $\alpha = 0.2$ level. The stratification factors will be the same as those used for the analyses of PFS and tumor response. The OS function for each randomized arm will be estimated using the Kaplan-Meier product-limit method. Median and two-sided 95% confidence intervals for median OS will be computed by randomized arm.

All analyses performed for PFS (detailed in [Section 7.5.1](#)) will be repeated for OS. Supportive analyses of PFS (detailed in [Section 7.5.1.1](#)) as well as the subset analyses (detailed in [Section 7.5.1.2](#)) will also be repeated for OS.

7.5.4 Currentness of PFS and OS Data

Time from last tumor assessment to data cut-off in months will be summarized by treatment arm and overall for all randomized subjects. Subjects who have a PFS event will be considered as current for this analysis. The primary (ITT) definition of PFS will be used for this summary.

Currentness of OS data will be summarized in months, by computing the time from “last known alive” date to data cut-off date. Subjects who have a death event will be considered as current for this analysis.

By-subject listings will also be produced to accompany the subject time from last tumor assessment table.

7.5.5 Efficacy Assessments

A by subject listing of efficacy will be provided to present the following:

- Percent change in serum and urine M-protein, from baseline and nadir.
- Serum free light chain kappa and lambda concentrations and the kappa/lambda ratio.
- Serum and urine immunofixation test results.
- Corrected calcium results
- Results of bone marrow analysis, including plasma cells (%) and clonality of plasma cells.
- Radiologic evaluation of extramedullary plasmacytoma and lytic bone lesions

In addition, a plot of the change in mean Serum and Urine M-protein per cycle will be presented.

7.6 Safety

Safety summaries will be based on the treated subject population, grouped by treatment regimen received. A subject's treatment regimen received will equal the arm to which the subject was assigned at randomization as long as he did not receive the wrong regimen throughout the study.

7.6.1 Adverse Events

AEs will be categorized using the most recent version of the MedDRA, by system organ class (SOC) and preferred term. The severity of AEs will be graded using the NCI CTCAE (v 3.0).

On-study AEs are defined as non-serious and serious AEs with an onset date on or after the first dose until 60 days after the last dose. See [Section 8.4](#), Imputing AE Onset Dates, for a discussion of imputation rules for incomplete or missing AE onset dates. If the relationship to study drug is missing, then the AE will be assumed to be related to study drug.

Unless specified otherwise, AEs will be counted only once per subject within each SOC and preferred term, according to their worst CTC grade.

Tables will be sorted by SOC and preferred term, with SOCs ordered by decreasing frequency overall and then alphabetically. Preferred terms will be sorted within SOCs by descending frequency overall and then alphabetically. The sorting will be done based on the total column when arms are presented side-by-side.

The following summaries will be presented by treatment arm:

Frequency tables of the worst grade of on-study AE will be presented: one table with AEs broken out by individual grade (1, 2, 3, 4 or 5) and an Any Grade category and another table in which both arms are included and grades are grouped as follows "Any, Grade 3-4 and Grade 5." The last summary will be repeated for:

- On-study drug-related AEs.
- On-study AEs that occurred \leq Cycle 2 and \geq Cycle 3.

A by-subject listing of all AEs will be presented.

- Exposure-adjusted AE incidence rates (including multiple occurrences of unique events) will be calculated for each SOC and preferred term.

Exposure-adjusted incidence rate per 100 person-years will be used and will be calculated as:

$$100 \times \left(\frac{\text{Total number of unique AEs}}{\frac{\text{subject date of last dose of study drug} - \text{subject date of first dose of study drug} + 60 + 1}{365.25}} \right)$$

and will be displayed along with a count of events

For these additional tables, AEs can be counted multiple times within each SOC and preferred term.

A by-subject listing of unique AEs will be provided.

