5.1 Progression-Free Survival

The primary objective of the study is to compare the progression-free survival between the treatment arms in all randomized subjects. The number of events and power of this study were calculated assuming an exponential distribution for PFS in each arm.

The study will require at least 71 PFS events (progressions or deaths), for a two-sided experiment-wise $\alpha = 0.2$ log-rank test, to show a statistically significant difference in PFS between the treatment arms with 85% power when the true hazard ratio of the experimental arm to the control arm is 0.57. This is equivalent to demonstrating an improvement in median PFS from 4.0 months in the Pd arm⁹ to a median PFS of 6.8 months in the E-Pd arm.¹ A total of 105 subjects are to be randomized. Assuming approximately 10% of subjects may be lost to follow-up for the primary endpoint data, an additional 9 subjects would be randomized in the study. It is estimated that it would take approximately 9 months for full accrual of 114 subjects (assuming a fixed accrual rate of 13 subjects per month) and another 6 months to obtain the required number of events.

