5.3 Overall Survival

OS is another secondary objective for this study. The final analysis of OS will be conducted after at least 78 deaths have been observed from 114 subjects. This is expected to happen 18 months (1.5 years) from the time of the final PFS analysis. With 78 events the study will have 75 % power using a two-sided log-rank test at a $\alpha = 0.2$ level, to show a statistically significant difference when the true hazard ratio is 0.64. This is equivalent to demonstrating a 56% improvement in median OS, i.e., 19.8 months in the E-Pd arm compared to the median OS in the Pd arm of 12.7 months.⁹

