7.6.3.3 Second Primary Malignancies

A summary table and a by-subject listing of second primary malignancies (SPM) will be provided. In addition, exposure-adjusted SPM incidence rates (including multiple occurrences of unique events) will be presented by treatment group and will be calculated as follows:

$$100 \times \frac{\text{Total number of unique SPM events}}{\left(\frac{\text{subject death date or last known alive date} - \text{subject date of first dose of study drug} + 1}{365.25} \right)}$$

Information on SPM will be obtained from the on-treatment eCRF page for secondary malignancies and the “Survival Status” eCRF page.

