8.4 Duration and Study Day Definition

In instances in which study period between two dates are to be calculated (for example, duration of response, PFS and OS), the convention to be used is as follows: later date – earlier date + 1 day.

Study day is calculated as assessment date – first dose date + 1 day, if the assessment is taken on or after the first dose day. If the assessment is taken prior to the first dose day, study day will be calculated as assessment date – first dose date. Date of first dose is defined as Study Day 1.

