8.6 AE, Laboratory Results and Concomitant Medication

Safety data will be handled according to the BMS safety data conventions (described in “Analysis of Safety Data - Reference to CT SOP 109”). This document includes descriptions on how to analyze AE data as well as how to handle partial dates, missing dates, and unknown end dates when analyzing safety data.

The following dictionaries will be used to code medical terms and to derive toxicity grades:

- Adverse events and other symptoms will be graded according to the NCI CTC Version 3.0 and categorized according to the latest version of MedDRA at the time of analysis.
- Laboratory results will be classified according to the CTC Version 3.0 grading system.

- All medications will be coded as per the latest version of the WHO Drug dictionary at the time of analysis.
- Tables and listings for laboratory results will be available in SI units and US units.

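### The exposure-adjusted AE rate counts 60 days after last dose for every subject, with no stop at death, last contact or data cut-off, so rates are modestly understated in both arms

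*SAP*

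**What the plan says.** SAP section 7.6.1 defines on-study AEs as those "with an onset date on or after the first dose until 60 days after the last dose". The exposure-adjusted rate per 100 person-years divides the number of unique AEs by the span from first to last dose, lengthened by a fixed amount ("subject date of first dose of study drug} + 60 + 1") and divided by 365.25. The single added day follows SAP section 8.4, where durations are "later date – earlier date + 1 day". The rate is planned for each system organ class and preferred term. The printed formula mentions neither death, nor last contact, nor data cut-off.

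Four other places bear on this:

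- The protocol synopsis keeps subjects on drug until progression, unacceptable toxicity or another stopping reason.
- SAP section 7.5 triggers the final PFS analysis at 71 or more events and says of it: "This analyses will serve as the basis for the clinical study report".
- SAP section 7.6.3.3 ends person-time for the second-malignancy rate at the "subject death date or last known alive date".
- SAP section 8.6 refers the handling of safety data to a separate convention document, which is not available here, and says: "This document includes descriptions on how to analyze AE data".

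**The concern.** A rate is sound when numerator and denominator cover the same observed time. Here the numerator is limited by what can be in the database, while the denominator runs 60 days past the last dose for everyone. Three groups contribute time in which no AE can be counted:

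1. subjects still on drug at the data cut-off, who add a full 60 days each;
2. subjects who stopped drug, but whose cut-off or last contact falls within the next 60 days;
3. subjects who die within 60 days of the last dose.

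Surplus days can only enlarge the denominator, so every affected rate is too low. Because the first two groups shrink as follow-up matures, the same true incidence would also read lower at the PFS analysis than at the OS analysis.

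What is at stake is the absolute level of a descriptive safety rate supporting the clinical study report. No hypothesis test depends on it, and the worst-grade frequency tables do not use this denominator.

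**Working it through.** The plan states no AE rate, so there is no figure to reproduce. The size can be derived from the plan's own design inputs.

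**Inputs from the SAP.** Section 5.1: median PFS 4.0 months (Pd) and 6.8 months (E-Pd), 114 subjects accrued at 13 per month over about 9 months, "and another 6 months to obtain the required number of events", so the cut-off is at 9 + 6 = 15 months. Section 5.3: median OS 12.7 and 19.8 months; for the OS analysis, "This is expected to happen 18 months (1.5 years) from the time of the final PFS analysis", so 15 + 18 = 33 months. Section 8.5: 30.4375 days per month.

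**Assumed, because the documents give no figure.** Equal allocation (57 per arm); 0–30% of PFS events are deaths; stopping before progression is either absent or exponential with a mean of 12 months; exponential survival after progression, set to match the OS medians; last dose equals the cut-off for subjects still on drug.

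**Step 1: cut-off alone, month 15, no early stopping.** Follow-up is uniform on 6 to 15 months. The PFS hazard is λ = ln 2 / median, or 0.1733 (Pd) and 0.1019 (E-Pd) per month. Sixty days is w = 60/30.4375 = 1.971 months.

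- Share still on drug, p = [exp(−6λ) − exp(−15λ)] / (9λ). Pd: (0.3536 − 0.0743)/1.5596 = 0.179. E-Pd: (0.5425 − 0.2168)/0.9174 = 0.355.
- Mean time on drug, (1 − p)/λ. Pd: 0.821/0.1733 = 4.74 months = 144 days. E-Pd: 0.645/0.1019 = 6.33 months = 193 days. Adding 61 days gives printed person-time of 205 and 254 days.
- Mean surplus days beyond the cut-off, p[exp(λw) − 1]/λ. Pd: 0.179 × 0.407/0.1733 = 0.421 months = 12.8 days. E-Pd: 0.355 × 0.2225/0.1019 = 0.775 months = 23.6 days.
- Understatement of the rate = surplus / printed person-time. Pd: 12.8/205 = 6.2%. E-Pd: 23.6/254 = 9.3%.

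With early stopping at a mean of 12 months, the same quantities fall to about 3.8% and 5.8%.

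**Step 2: add the stop at death.** This was simulated with 400,000 subjects per arm. Understatement is 1 − (capped person-time / printed person-time), where capped person-time ends at the earliest of last dose + 60 days, death and cut-off. With 15% of PFS events being deaths and no early stopping, mean printed against capped days at month 15 are 205 against 183 in Pd (about 11%) and 254 against 223 in E-Pd (about 12%). Across all assumed death shares and both stopping patterns:

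| Cut-off | Pd understated | E-Pd understated | E-Pd:Pd rate ratio multiplied by |
|---|---|---|---|
| Month 15 (planned PFS analysis) | 6–14% | 7–14% | 0.98–1.01 |
| Month 33 (OS analysis) | 2–9% | 1–6% | 1.00–1.03 |

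**Step 3: event-driven cut-off.** The PFS analysis is triggered by events, not by date. At month 15 the expected count is 57 × 0.821 + 57 × 0.645 = 83.6, more than 71. With 114 subjects, 71 events are expected at about month 12.2 to 12.3. There the understatement is about 10–19% across the two arms, with a ratio factor of 0.98–1.01.

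**Why the ratio barely moves.** At month 15 about 8–18% of Pd and 16–36% of E-Pd subjects are still on drug, while about 12–31% of Pd and 6–23% of E-Pd subjects have died within 60 days of the last dose. The two mechanisms load on opposite arms and largely cancel, so the direction of the residual effect on the ratio cannot be stated in advance.

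**The case against.** **The separate safety convention document may already define a stop.** This cannot be ruled out, and it limits what can be claimed: the printed SAP formula lacks a stop, and rates computed as printed will be too low. It does not remove the point, because a programmer will implement an explicit formula as written, and nothing beside it points elsewhere for person-time.

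**The formula is shorthand.** It shows no sum over subjects, and neither does the second-malignancy formula, so details are evidently left to programming. That is fair, but it is a reason to write the denominator out in full.

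**The second-malignancy rate is not a true comparator.** Protocol section 5.4.1 follows second malignancies along with survival after progression, so ending at death or last known alive is that endpoint's own risk period. This stands: the difference between the two formulas is not in itself an inconsistency. What section 7.6.3.3 does show is that the dates needed are already in use.

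**The rates are descriptive.** This also stands. The between-arm ratio shifts by 3% or less, event counts appear beside the rates, the main safety tables are unaffected, and the rates are not among the top-line outputs listed in SAP section 8.7. It limits the importance of the point; the absolute rates remain too low.

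**The size rests on assumed inputs.** This is true of the part due to deaths. The cut-off part in Step 1 needs only the SAP's PFS medians and accrual, plus the treatment of last dose and early stopping stated there.

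**Conclusion.** The concern holds. As printed, the denominator includes time in which no AE can be recorded, and the direction of the error follows from the formula alone. Under the design assumptions and the labelled assumptions on deaths and early stopping, rates are understated by about 6–14% at the planned 15-month PFS analysis, about 10–19% if 71 events arrive near month 12, and 1–9% at the OS analysis. Loss to follow-up was not modelled and would add to the shortfall. The comparison between arms is nearly unaffected, with a ratio factor of 0.98 to 1.03. This is a modest error in a descriptive table, worth correcting because it runs one way and is cheap to remove. The one thing that could settle it without a change of method is a stop rule already written in the separate safety convention document.

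**What to change.** Replace the denominator in SAP section 7.6.1 with person-time per subject equal to min(last dose + 60 days, death date, last contact date, data cut-off date) − first dose date + 1. Sum this over the subjects in the arm, divide by 365.25, and count only AEs with onset in that same window. If the safety convention document already applies such a stop, cite it beside the formula.

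The cost is one formula and its programming. Death and last known alive dates are already used in section 7.6.3.3, and the data cut-off date in section 7.5.4. No new data collection or design change is needed.
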